## 4.0 Design and Procedures

This is a phase III, 18-month, 3-arm randomized controlled trial. Extending from the core component of the EMPOWER-I intervention (targeted mailed educational materials) we will evaluate the utility of patient activation with and without added PCP activation. Data will be collected at baseline and approximately 18-months through patient and provider surveys and medical record review. The primary outcome will be a self-reported breast MRI and mammogram.

The baseline and end-of-study surveys will be self-administered through the Eureka app. Non-compliant participants will be given an option to complete the surveys online through a link sent via email and push notification. A follow-up push notification and email will be sent for non-responders. If the participants are unable to complete the app or online surveys after automated and email reminders, the CCSS Coordinating Center will administer the questionnaires over the phone. A print option via regular mail, followed by a phone call from the study team, will be sent as a final attempt to collect survey data. The questions pertaining to socio-demographics, general health status, health care access, and health and cancer screening practices are standard CCSS items. Considering potential technical issues as well as the effects of the COVID-19 pandemic, follow-up of end-of-study data may take a few months to allow patients to return completed surveys and qualitative interviews.

## EMPOWER-II

A final attempt to collect study outcomes (mammogram, breast MRI, breast ultrasound, medical records and pathology) from 63 participants who are more than 3 months past the approximated 18-month study window will be done via 2 regular mailings, an email notification (sent by the Duke team), and a follow-up phone call from the CCSS Coordinating Center who will administer the questionnaires over the phone. The mailed packet will include 2 options to complete the end-of-study survey: a) a full survey set or b) an abbreviated version of the survey focusing on the main study outcomes (i.e. were they able to get their breast cancer screening tests done and where). PCP factors will also be collected for this group. This attempt extends this group's participation by up to a year. These participants have already completed the baseline survey but have not responded to multiple automated and email reminders within the initial 18-month study period. This extended timeline will not be applicable to those who are currently active in the study.

To collect information on PCP factors, the Duke team will administer the baseline and end-of-study surveys (print via fax) for the PCPs of the CCSS participants. We will ask women in the baseline survey for the name and contact information for their PCP and will solicit this information via the Eureka app for those who don't have one at baseline.

After completion of the baseline measurement questionnaire, participants will be randomly assigned, in a ratio of 1:1:1, to one of the three groups: control, patient activation (PA), or patient activation + primary care provider activation (PA+PCP). An overview of the 3 groups is presented in **Appendix I**. All participants will receive the mailed education materials used in EMPOWER-I.

Recurring notifications, sent through the Eureka App, will be added to remind participants of pending study activities. Also, a cost sharing survey and a Eureka App user experience survey will be added to the End of Study Questionnaire.

This study will use a 3-group comparative effectiveness design comparing:

- Targeted mailed educational materials (C) including a Survivorship Care Plan;
- C + patient activation (PA) consisting of (1) a HIPAA compliant smartphone app that will be used to administer surveys and provide electronic copies of breast cancer screening resources; and (2) tailored push notifications and app messages with links to video vignettes discussing the primary barriers to breast MRI and mammography identified by participants in EMPOWER-I;
- C + PA + PCP activation (PA+PCP) with physician materials about breast cancer risk in this population along with national and international guidelines for breast cancer surveillance.

Specific intervention components are explained in greater detail in **Appendix II**. During the developmental stages for this study, our Patient and PCP Advisory Boards provided recommendations for the interventions and study materials. A summary of their feedback can be found in **Appendix III**.

### COVID-19 Response

Study outcomes may be affected by the loss of jobs and/or health insurance of study participants due to the COVID-19 pandemic. In light of this, the study period for participants who consented or who received a study invitation prior to the COVID recruitment hold will be extended to 18 months. These participants will receive their end-of-study survey through the Eureka app once they complete their screening tests (mammogram and/or breast MRI) or at approximately 18 months, whichever is sooner. An email from the Principal Investigator will be sent to current participants informing them of this change.

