## EMPOWER-II

2.1.1 To determine the effectiveness of PA+PCP compared to PA on breast cancer surveillance rates (breast MRI + mammogram).

2.1.2 To determine the effectiveness of the two interventions on rates of each individual surveillance test: breast MRI or mammography.

2.1.3 To explore moderating and mediating patient and PCP-level factors (from baseline and end-of-study surveys of participants and their PCPs) that predict breast MRI and mammography completion and timing of the obtained surveillance. The 12-month follow-up surveys have been postponed to approximately 18 months to acknowledge the COVID-19 impact on screening availability and feasibility for participants at this time. This change is reflected in all responses regarding the 12-month survey throughout this protocol.

2.1.4 To estimate (1) the replication costs of the interventions and (2) costs resulting from the interventions.

2.1.5a Annotate the repository with sociodemographics of the women, radiation dose/field, and measures of ovarian function, and imaging modality.

2.1.5b Utilize the Mazurowski method of deep learning-based segmentation for normalization of the breast MRIs.

2.1.6 Characterize mammographic breast density, by single-reader radiology review and by semi-manual, semi-automated computer software (Cumulus), in childhood cancer survivors using the breast imaging repository and compare to the mammographic breast density in a cohort of women without a history of cancer and undergoing routine breast mammography, matched 1:3 for age at study, calendar year of mammogram, race/ethnicity, and menopausal status.

2.1.7 Measure BPE on breast MRIs, by single-reader radiology review and by computer-based algorithm, in the repository and compare to a cohort of high-risk women without a prior cancer who are undergoing breast cancer screening with breast MRI; match 1:2 for age at study, calendar year of breast MRI, race/ethnicity, and menopausal status.

2.1.8 Gather exploratory information regarding participant's insurance coverage, cost burdens related to recommended screening practices, and how this burden influences screening engagement.

2.1.9 Explore how participant's past, present, and future screening behaviors may have been impacted by the COVID-19 pandemic, as well as how they have been engaging in telehealth and other alternative options during this time.

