### 5.1 Primary and Secondary Outcomes:

The following items were developed in 'Mammography and High-Risk Survivors of Pediatric Cancer' (R21 CA106972; PI: [name]) and refined for EMPOWER-I (R01CA134722).

- Breast MRI practices: Items that characterize breast MRI practices, including a differentiation between screening and diagnostic breast MRI and barriers to having an MRI.
- Mammogram practices: Items that characterize mammogram practices, including a differentiation between screening and diagnostic mammography and barriers to having a mammogram.
- Ascertainment of the primary and secondary breast cancer surveillance outcomes: The primary outcome will be a self-reported breast MRI and mammogram. If a survivor reports that she has had a breast MRI and/or a mammogram, she will be asked the contact information for the imaging center. We will then contact the imaging center, provide the signed medical record release form (from enrollment), and request a faxed copy of the imaging report(s).
- Descriptive data on physician visits, abnormal imaging studies, biopsies and cancers: In the end-of-study survey, participants will be asked to describe all medical visits during the study period, including routine non-procedure breast-related visits. Women who have had a mammogram and a breast MRI or ultrasound will be asked if they had an abnormal imaging study and the follow-up procedures for this imaging study. As per CCSS standards, if a woman reports a breast cancer, we will seek copies of the pathology and operative reports and provide this information to the CCSS Pathology Center.

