## EMPOWER-II

participants and study teams) with a granular password protected user permissions system. The Eureka Privacy Policy and Data Security Measures agreement document has been uploaded into the eIRB. This is the IRB-approved policy all participants will have to agree to as part of the app registration process.

Our goal is to develop an inexpensive set of automated tailored notifications, video vignettes, and materials that do not rely on personnel time and thus can more easily be disseminated. The overarching goal of this approach is to activate the participant to make an appointment with her PCP and to discuss, request, and obtain breast cancer screening. We have also incorporated a reminder strategy in the push notifications and app messages.

The push notifications, app messages, and video vignettes are based upon an algorithm that is highly tailored in content (e.g., history of prior screening, specific barriers, etc.) and timing (e.g., will be informed by the timing of decision-making mapped to the behaviors being encouraged) and will ask specific questions (e.g., do you have a PCP, have you had a breast MRI and/or mammogram in the last 12 months, have you ever had a breast imaging study, do you have an appointment with PCP and when). The information sent via the Eureka app will be tailored to participants' answers. The number of push notifications and app messages that a participant receives will be variable, will occur at least monthly until screening is completed (based upon their responses), and will include:

EMPOWER-II IN-APP & SMS TEXT MESSAGES	
POST-RANDOMIZATION: INTERVENTION & CONTROL	
Text message: Welcome to the EMPOWER study! You will be receiving information on resources for breast cancer screening in the mail soon. Thank you for your participation!	
IN-APP TEXT: Self-management Survey Please answer the following questions about your health.	
IN-APP TEXT: Mammogram Survey Please answer the following questions about getting a mammogram.	
INTERVENTION	
IN-APP TEXT: The information that we sent you in the mail about breast cancer screening may also be accessed electronically through this link (link to LTFU website).Please click the link below and watch this brief Welcome video -Video 1	
IN-APP TEXT: Click the link below: -Video 2	
IN-APP TEXT: Please fill out a brief survey. -> Takes the user to:	
SURVEY ACTIVITY	

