Have you had BOTH an MRI and mammogram since receiving your EMPOWER packet or in the last 12 months? -YES -> survey activity: screening -NO ->PCP question and monthly MRI/mammogram reminders (parallel tracks sent 2 weeks between each other)	
IN-APP TEXT: We are happy that you have completed BOTH your breast MRI and mammogram. We have 5 questions for you. Please update your information in the next survey:	
SURVEY ACTIVITY	
When did you get your mammogram?	

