### When did you get your breast MRI?

-MM/YEAR

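### One test can trigger the only outcome survey although the primary outcome needs two, and no date window says which tests count

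*Combined protocol and SAP*

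**What the plan says.** Section 5.1 defines the endpoint: "The primary outcome will be a self-reported breast MRI and mammogram". Section 6.0 analyses the proportion of women with both, and Sections 6.0 and 6.1 count a woman with no end-of-study assessment as a failure.

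Section 4.0 describes two data collections: "Data will be collected at baseline and approximately 18-months through patient and provider surveys and medical record review". Section 2.1.3 gives the history: "The 12-month follow-up surveys have been postponed to approximately 18 months".

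The COVID-19 Response text then adds a rule for part of the sample. It says the study period for "participants who consented or who received a study invitation prior to the COVID recruitment hold will be extended to 18 months", and that these women get the end-of-study survey "once they complete their screening tests (mammogram and/or breast MRI) or at approximately 18 months, whichever is sooner".

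Section 4.0 also allows final data collection to run a few months late for participants generally. It describes a last attempt to obtain outcomes from 63 women already more than 3 months past the 18-month window. Their participation is extended by up to a year, and women still active do not get this extension. One option offered to the 63 is a short form, summarised as asking whether the tests were done and where.

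In Appendix II, the intervention messages repeatedly ask "Have you had BOTH an MRI and mammogram since receiving your EMPOWER packet or in the last 12 months". A yes leads to items such as "When did you get your breast MRI". The control messages contain no such items, only links and calendar reminders of the final survey.

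**The concern.** Two things are unsettled for the primary endpoint.

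First, the survey trigger and the endpoint do not match. The endpoint needs two tests, but the and/or in the trigger lets one test close a woman's outcome assessment. If she is surveyed after a mammogram in month 5 and has her MRI in month 9, the only described outcome survey records one test and she counts as a failure. The failure rule in Sections 6.0 and 6.1 does not address her, because she did return a survey.

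Second, nothing says by when the two tests must have been done. Women who report late could have tests after month 18 counted, while women surveyed on time could not. The primary proportion would then be measured over unequal periods.

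At stake are lost power, a possible bias toward no effect if early surveys arise mainly in the intervention arms, and absolute screening rates that do not refer to a common period.

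**Working it through.** **Inputs from the documents.** Control rate 10%, difference 20 points, two-sided type I error 0.025 per comparison (Section 6.2). Table 1 gives 90% power for 10% versus 30%. Section 3.0 gives two sample sizes: three waves of 97, so 291 in all or 97 per arm, and a randomisation target of 320, so 320/3 = 106.7 per arm.

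**Formula.** Pooled two-proportion normal approximation, with p̄ = (p1 + p2)/2 and z = 2.2414:

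power = Φ{ [(p2 − p1) − z·√(2p̄(1 − p̄)/n)] / √[p1(1 − p1)/n + p2(1 − p2)/n] }

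**Plan's own figure.** For 10% versus 30% at n = 97: (0.20 − 2.2414 × 0.05744)/0.05561 = 1.281, so power is 0.900. This matches Table 1. At n = 106.7 it is (0.20 − 2.2414 × 0.05477)/0.05303 = 1.457, or 0.927. At 97 per arm, the 10% versus 28% row also reproduces (0.836 against 83%). The 15% versus 35% row does not (0.842 against 80%), but nothing here depends on it.

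**Loss from the one-test trigger (assumed rates).** Let f be the share of an arm's true both-test completers who are surveyed after the first test and not asked again. The observed rate in that arm is p(1 − f). The documents do not give f, so 10% and 25% are illustrations.

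| f | Where | Observed rates | Difference | Power, 97/arm | Power, 106.7/arm |
|---|---|---|---|---|---|
| 0 | none | 10% vs 30% | 20.0 | 0.900 | 0.927 |
| 10% | both arms | 9% vs 27% | 18.0 | 0.853 | 0.888 |
| 10% | intervention only | 10% vs 27% | 17.0 | 0.796 | 0.836 |
| 25% | both arms | 7.5% vs 22.5% | 15.0 | 0.758 | 0.801 |
| 25% | intervention only | 10% vs 22.5% | 12.5 | 0.548 | 0.593 |

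The rule covers only women consented or invited before the hold, and their number is not given. If it covers half an arm and 20% of the covered completers are lost, then f = 0.5 × 20% = 10%. If a both-test trigger is what operates, f = 0.

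The intervention-only rows are included because Appendix II lists completion prompts only for the intervention arms. Reports that could set off an early survey may therefore come mainly from those arms.

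**Late collection.** 63/320 = 19.7%. Suppose 50% of the 63 reply and 20% of the repliers completed both tests only after month 18. That is 63 × 0.50 × 0.20 = 6.3 women, or 2.0 points of 320. With 25% replying and 10% late it is 63 × 0.25 × 0.10 = 1.6 women (0.5 points). With 75% and 30% it is 63 × 0.75 × 0.30 = 14.2 women (4.4 points). If the 63 split evenly (21 per arm) with equal late shares, both arms rise equally. The difference is unchanged and the null rejection rate stays at 0.025. An uneven split would move the difference, but the documents give no split.

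**The case against.** The strongest reply is that a both-test trigger is what was meant. The rule speaks of tests in the plural, the app items ask about both, and Appendix II keeps reminders going until screening is completed. On that reading an early survey follows only success and costs nothing. This is plausible, but the rule that governs survey dispatch does not say it.

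A reader might go further and call the COVID-19 rule and Appendix II contradictory. The documents do not support that. The app items govern messaging: a yes opens questions on dates, facilities and the ordering provider, not the end-of-study survey. What stands is an ambiguous trigger.

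A reader might also infer that test dates are not collected outside the intervention app. That is not shown. Sections 2.0 and 2.1.3 plan to study the timing of surveillance, the full end-of-study survey is not reproduced, and the short form is known only from a brief summary. Section 5.1 requests imaging reports for reported tests, Section 4.0 seeks medical records from the 63, and Section 6.0 plans a secondary analysis of fax-confirmed imaging. So the dates may well exist. What is missing is a rule that uses them.

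Nor are the 63 simply favoured over everyone else, because Section 4.0 lets collection run a few months late for participants generally. The open window applies to the whole trial and is longest for the 63.

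Finally, Section 3.1 excludes women who had both tests in the previous 24 months, so a complete pair from before entry should not arise. A single earlier test is allowed, however, and a 12-month look-back can reach before randomisation.

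**Conclusion.** The point holds in this form. As worded, the COVID-19 rule lets one test trigger the only described survey for a two-test primary outcome, with no repeat question. No section sets a test-date window for that outcome. Following the stated rules can therefore misclassify the primary endpoint.

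The size cannot be found from the documents. Under the assumed losses of 10% to 25% of both-test completers, power at 97 per arm falls from 0.900 to between 0.853 and 0.758 with equal loss, and to between 0.796 and 0.548 with loss in the intervention arm only. Loss confined to the intervention arm would bias toward the null, but the documents do not show that it occurs. If the trigger in practice is both tests, this loss is nil.

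Counting late tests would add about 0.5 to 4.4 points to the overall rate under the assumed ranges. With an even split it mainly shifts absolute rates. The documents do not support a claim that late collection inflates the type I error.

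This should be settled before the primary analysis.

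**What to change.** 1. Reword the COVID-19 Response rule so the end-of-study survey goes out after both tests or at month 18, whichever is sooner. Ask again any woman surveyed after one test. Do this at month 18 or, if that has passed, at the final contact, asking about tests done by month 18.
2. In Sections 5.1 and 6.0, count success only if both tests are dated after randomisation and within 18 months of it, in every arm and whenever the survey is returned. Report later tests in a sensitivity analysis. Section 1.0 gives annual imaging as the standard, so a test done before entry falls due again inside this window.
3. Make sure every survey version, including the short form, asks the month and year of each test. The app item can be reused. Where a date is missing or falls in the boundary month, use the imaging report already requested. If the test is still undated, count it as reported in the primary analysis and as a failure in a sensitivity analysis.
4. Extend the planned fax-confirmed analysis to check dates and second tests, and report survey timing by arm.

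The cost is protocol and SAP wording, a date item where one is lacking, and a short repeat contact. No new participants are needed. The downside is that some late completions stop counting: about 2 to 14 women among the 63 under the ranges assumed above.

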## 6.0 Statistical Analyses

The primary analysis involves comparing the proportion of women with a self-reported breast MRI and mammogram in each intervention arm to C. In EMPOWER-I, we used self-report of the imaging studies. We also sought to obtain medical record (fax) confirmation of the self-reported imaging studies. We were successful in obtaining the proper reports for 85.7% of the participants. However, for the remaining 14.3%, we were unable to confirm the study due to lack of information provided by the participant regarding the imaging facility, the imaging facility being unable to locate records and the facility sending only partial information, despite multiple attempts to collect the data. Importantly, the findings were not substantively different when we repeated the analysis including only women with a fax-confirmed imaging study. Stratifying on the randomization strata, differences in these proportions will be estimated with stratum-adjusted proportions calculated using the weighted average of the stratum-specific differences and accounting for the sampling scheme. The Cochran-Mantel-Haenszel test will be used to test for differences between (1) PA and C, and (2) PA+PCP and C in an intent-to-treat analysis where women who do not complete the end-of-study assessment will be counted as not having had a breast MRI and mammogram. We will also perform a secondary analysis of women with a fax-confirmed imaging study. Based on EMPOWER 1 results, we do not expect results to differ based on race/ethnicity, but will verify this result here. The analytic methods for the secondary objectives will be the same as for the primary objective, using the Cochran-Manetel-Haenszel test to examine differences between the interventions (PA, PA+PCP) on breast cancer surveillance rates (breast MRI + mammogram) and on rates of each individual surveillance test.

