## EMPOWER-II

CONTROL
IN-APP TEXT: The information we sent you in the mail about breast cancer screening may also be accessed electronically through the link below: -link to LTFU website
Text message: Click here to stay up to date with LTFU news -link to LTFU newsletter and resource page
Text message: This is a reminder that you will be receiving your End of Study EMPOWER Survey in about another 6 months from now. Please complete the survey upon receipt. Thank you for your continued participation in the EMPOWER study!
Text message: This is a reminder that you will be receiving your End of Study EMPOWER Survey in 2 weeks. Please complete the survey when you get it. Thank you for participating in the EMPOWER study!
IN-APP TEXT: End of Study Survey Please answer the following questions about your health.

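### For women in the pre-hold group, screening can trigger the end-of-study survey early, but the only scheduled completion check is in PA and PA+PCP, so outcome timing and capture can differ by arm, in either direction

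*Combined protocol and SAP*

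**What the plan says.** Section 4.0, COVID-19 Response, extends the study period to 18 months for "participants who consented or who received a study invitation prior to the COVID recruitment hold". These women receive the final survey "once they complete their screening tests (mammogram and/or breast MRI) or at approximately 18 months, whichever is sooner". The rule names no arm and does not say how the study learns that screening is done. It adds: "An email from the Principal Investigator will be sent to current participants informing them of this change".

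The Appendix II message table sets out two streams after randomisation. The intervention stream asks "Have you had BOTH an MRI and mammogram since receiving your EMPOWER packet or in the last 12 months" and repeats the question in the cost, priority and symptom modules. The Appendix II text has messages going out at least monthly until screening is done. A yes leads to "We are happy that you have completed BOTH your breast MRI and mammogram" and then to questions on when and where each test was done. The control stream has a link to the materials, a newsletter link, two calendar-timed reminders (one reads "This is a reminder that you will be receiving your End of Study EMPOWER Survey in about another 6 months from now") and the final survey. It has no completion question and no facility form. A mammogram survey listed for both streams after randomisation is not a recurring check.

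Section 5.1 makes the primary outcome a self-report of both tests. Under Section 6.0, "women who do not complete the end-of-study assessment will be counted as not having had a breast MRI and mammogram"; Section 6.1 repeats this.

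**The concern.** The time at which a woman is asked for her outcome can depend on the outcome itself, and the scheduled means of learning about that outcome exists in two arms only. A PA or PA+PCP woman who is screened early has a scheduled occasion to say so, and may be surveyed while she is engaged. A control woman screened at the same time has no scheduled occasion before about month 18. If more successes are lost at the later contact, scoring non-response as failure turns the difference in procedure into a difference in rates in both primary comparisons. The completers-only analysis in Section 6.1 would not remove this, because early surveys sent on completion would enrich the intervention completers with successes.

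The opposite error is also possible. The trigger is met by one test, while the endpoint and the in-app question need both. If the final survey goes out after the first test and closes follow-up, a later second test is missed. That would fall mainly on the arms where completion is more readily detected.

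**Working it through.** **1. The plan's own figure.** The documents give no number for the survey trigger, so Table 1 serves to check the test model. For 10% v 30% at two-sided 0.025 (Section 6.2), pooled two-proportion z test, 97 per arm:
- null SE = √(2 × 0.20 × 0.80 / 97) = 0.0574
- alternative SE = √((0.09 + 0.21) / 97) = 0.0556
- (0.20 − 2.241 × 0.0574) / 0.0556 = 1.28, so power is 90.0% (stated: 90%)

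Section 3.0 gives both 320 women (about 107 per arm) and three waves of 97 (291, or 97 per arm). At 320/3 per arm the same formula gives 92.7%. The illustration below uses 107 per arm, with 97 as a check.

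**2. The two streams side by side.**

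| | PA, PA+PCP | Control |
|---|---|---|
| Recurring completion question | yes | none listed |
| Form for test dates and facilities | yes, on a yes answer | none listed before the final survey |
| Reminders of the final survey | yes | yes, calendar-timed |
| Early-survey rule (Section 4.0) | applies | applies, with no scheduled detection |

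**3. Bias towards the interventions.** Observed rate = true rate × share of successes captured. A pure delay with full capture changes nothing; only unequal loss does.

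Assumptions: no true effect; control capture 80%; intervention capture 95-100%; all women affected. The 80% borrows from the 63 women in Section 4.0 who are more than 3 months overdue (63/320 = 19.7%). That count is not split by arm and was taken before the final retrieval attempt. The table gives the exact binomial probability of a significant result favouring the intervention, ignoring stratification. The nominal value is 0.025/2 = 1.25%.

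| True rate | Observed control | Observed intervention | False gain (points) | False win, 107/arm | False win, 97/arm |
|---|---|---|---|---|---|
| 10% | 8% | 9.5-10% | 1.5-2 | 3.2-4.1% | 2.9-3.7% |
| 20% | 16% | 19-20% | 3-4 | 4.9-7.0% | 4.5-6.4% |
| 30% | 24% | 28.5-30% | 4.5-6 | 6.7-10.5% | 6.4-9.8% |

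With equal capture of 80% in both arms, the false-win rate at 107 per arm stays at 1.2-1.3%.

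**4. Partial coverage.** The size of the pre-hold group is not given. If the rule reaches half the women, intervention capture is 0.5 × 1.00 + 0.5 × 0.80 = 0.90. At a true rate of 20% the observed rates are 16% v 18%, and the false-win rate at 107 per arm is 3.3% instead of 7.0%.

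**5. Bias against the interventions.** Take the design case of 10% v 30%, and assume that 10% to 19.7% of intervention successes are missed because follow-up closes after one test:
- 0.30 × 0.90 = 27.0%, a difference of 17.0 points; power at 97 per arm 79.6%
- 0.30 × 0.803 = 24.1%, a difference of 14.1 points; power at 97 per arm 64.6%

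For comparison, losing 19.7% of control successes in the same design case moves the difference only from 20.0 to 22.0 points (30% − 8.03%).

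**The case against.** A reader might infer that the early survey can go only to PA and PA+PCP women, and that their successes are recorded at once. The documents do not support that. The rule covers every arm and gives no detection route. Current participants are told of it by e-mail, so a control woman could report completion herself. No text links the in-app yes to the final survey: it leads to a separate form. The rule also covers only the pre-hold group.

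A reader might also infer that control successes are certainly lost more often. Asking at month 18 about a test at month 4 loses nothing if the woman answers. Section 4.0 provides reminders, an online link, telephone and print, without distinction by arm. For the 63 overdue women it adds two mailings, an e-mail, a call and an abbreviated survey. Nothing shows that those women are mostly controls or hold successes at the usual rate. At the planned control rate of 10%, the assumed gain is 1.5-2 points against a design difference of 20. Nor do the documents say that in-app answers count as outcome data. Fax confirmation feeds a secondary analysis, and Section 5.1 seeks facility details from any woman who reports a test.

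All of this stands as a limit on direction and size. It does not remove the asymmetry in the schedule, or the mismatch between a trigger that one test satisfies and an endpoint that needs two.

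**Conclusion.** The point holds as a risk of arm-dependent outcome measurement, not as a demonstrated bias. For the pre-hold group, survey timing can depend on the outcome, and the only scheduled completion check is in the intervention arms. With self-report and non-response scored as failure, capture can then differ by arm.

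Neither direction nor size is fixed by the documents. Under the assumed capture rates (80% v 95-100%, all women affected, about 107 per arm), the false-win chance per comparison rises from about 1.25% to 3-4% at a true rate of 10% and 5-7% at 20%; it is smaller with partial coverage. Under the opposite assumption, a true 20-point difference shrinks to 17.0-14.1 points. This should be fixed. It does not by itself invalidate the trial.

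**What to change.** - Assess the primary outcome (both tests, with dates) at the same fixed time after randomisation in C, PA and PA+PCP, and count tests by date within that common window.
- Do not let a completion report, or one test alone, close outcome follow-up. Reconcile the either-test trigger with the both-tests endpoint.
- Re-ask women already surveyed early the abbreviated outcome items from Section 4.0 at the common time. Because test dates are asked, this also works for women already past it.
- State how completion is detected in each arm. Do not use in-app completion answers as outcome data: control has no such question, and its 12-month look-back can reach before randomisation.
- Report survey timing and non-response by arm.

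The cost is protocol wording, app scheduling and one short repeat contact for early responders. Giving control the same recurring dates-and-facility form is a weaker alternative, because repeated questions about screening may prompt control women to be screened and dilute the contrast.
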